¹Baseline assessments may be performed on the same day where considered logistically and clinically appropriate. All assessments should be performed as soon as possible; however, all baseline assessments must be done within a 3 month period.

²Additional baseline assessments are permitted if there is inconsistency between the screening and first baseline assessment

³Measurements for vital signs include: blood pressure, pulse, respiration rate, arterial oxygen saturation, temperature, height and weight

⁴Visual acuity at day 1 and 3 will be assessed using the previous refraction.

⁵ERG assessments may be performed under general anaesthesia if considered appropriate

⁶ HBV testing is only mandatory for participants if required by local practice. Participants with chronic hepatitis B virus infection as indicated by detectable surface antigen will be excluded from the study. For those with negative surface antigen, but positive hepatitis B core antibody, testing will be performed to confirm Hepatitis B viral load following completion of steroid treatment.

⁷ Additional monitoring of liver enzymes will be performed following steroid treatment

⁸ Patients who screened failed under a previous version of the protocol may be reconsidered for eligibility and will not be required to repeat tests provided these were performed within the visit window from the original screening date.

⁹ Two Treatment Experience interviews will be administered to the low and intermediate dose active treatment group at 6 months (Visit 14) and at 12 months post-treatment (either at the visit or within 14 days of the final study visit - visit 16), or upon early withdrawal.

*Per section 5.4.2.1 assessments listed as "performed in all participants" must be performed, every effort must be made to perform all other assessments where possible

Table 4: Trial Assessments (Deferred Treatment arm) *

, unic ii		nts (Deferred				uring	ř –			 	· · · ·	ř	· · · · ·				_
	Up to 4 months prior to randomisation	Randomisation	Ва	Baseline ^{1, 2}		M3 ⁸	M6 ⁸	ATIMP admin after M6 assessments	D1 post- ATIMP admin	D3 post- ATIMP admin	W1 post- ATIMP admin	W2 post- ATIMP admin	W4 post- ATIMP admin	W6 post- ATIMP admin	W9 post- ATIMP admin	M3 post ATIMP admin	M6 post ATIMP admin
Flexibility of schedule (+ days)			8			± 14D	14D	+14D	+ 0D	+ 1D	+ 2D	+ 4D	+ 7D	+ 7D	± 7D	± 14D	± 14D
Visit number	1		2	3	4	5	6	7	8	9	10	11	12	13	14	15	16

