Informed consent	•																
Physical exam	•																es.
Medical history	•					•				7	•		•	•		•	•
Eligibility determination	•						•										
IMP administration								*			70	(ç					
Adverse event review			•	•	•	•	•		S A	•		•	•	•	•	S	
Concomitant medication review	v.		•	● R	•	•	•		•8	•	•	•	•	•	3. T	• 3	
Genetic screening	•	9									10	20			3		3
Vital signs (including height and weight) ³	•		•				•		•8		•	•	•	•			
Randomisation		*										9.					ō.
Haematology			•						•33		•13		•	(• X			
Biochemistry/ glucose			•)•				•.1	•	•	•	•7		
Hepatitis B (HBV) testing ⁶	•																
Serology		,	•			8						10 01	•			•	•
PCR													•				

	Up to 4 months prior to randomisation	Randomisation	Ba	Baseline ^{1, 2}		M3 ⁸	M6 ⁸	ATIMP admin after M6 assessments	D1 post- ATIMP admin	D3 post- ATIMP admin	W1 post- ATIMP admin	W2 post- ATIMP admin	W4 post- ATIMP admin	W6 post- ATIMP admin	W9 post- ATIMP admin	M3 post ATIMP admin	M6 post ATIMP admin
Flexibility of schedule (+ days)						± 14D	14D	+14D	+ 0D	+ 1D	+ 2D	+ 4D	+ 7D	+ 7D	± 7D	± 14D	± 14D
QoL questionnaires (IVI, EQ5D-5L, EQ5D- Y, Low Luminance Questionnaire), Patient Global Impression of Severity			•				•									•	•
Patient Global Impression of Change and Clinician Impression of Change												9					•
Treatment Experience Interview ¹⁰																	•
Visual acuity ⁴			•	•	•	•	•		•8		•)	•	•	(•)(•	
Low Luminance Visual Acuity			•	•	•											•	•
Contrast sensitivity			•	•	•	•	•			ra s	75	£6			24	•8	
Reading speed Colour vision assessments		2	•	•	•	•	•	3					S 5-			•	•
Static visual fields			•	•	•	•	•					65	· V.			•	
Microperimetry			•	•	•	•	•					i i				•	•
Ocular examination			•	•	•	•	•		•	•	•	•	•	•	•	•	•
Fundus photography			•			•	•		•	***	•		•	•	**•		•

	Up to 4 months prior to randomisation	Randomisation	Ba	Baseline ^{1, 2}		M3 ⁸	M6 ⁸	ATIMP admin after M6 assessments	D1 post- ATIMP admin	D3 post- ATIMP admin	W1 post- ATIMP admin	W2 post- ATIMP admin	W4 post- ATIMP admin	W6 post- ATIMP admin	W9 post- ATIMP admin	M3 post ATIMP admin	M6 post ATIMP admin
Flexibility of schedule (+ days)						± 14D	14D	+14D	+ 0D	+ 1D	+ 2D	+ 4D	+ 7D	+ 7D	± 7D	± 14D	± 14D
Optical coherence tomography	•		•	•	•	•	•		100 S	•	•		•				
Adaptive optics imaging			•				•										•
Fundus autofluorescence			•	•	•	•	•			2						•	
Full field electroretinography ⁵			•			•											•

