Pattern electroretinography ⁵			•			•											•
Multifocal electroretinography ⁵			•			•											
Visual mobility assessment ^{8 9}	•					ě	•								ii	•	•

¹Baseline assessments may be performed on the same day where considered logistically and clinically appropriate. All assessments should be performed as soon as possible however all baseline assessments must be done within a 4 month period.

²Additional baseline assessments are permitted if there is inconsistency between the screening and first baseline assessment

³Measurements for vital signs include: blood pressure, pulse, respiration rate, arterial oxygen saturation, temperature, height and weight

⁴ Visual acuity at day 1 and 3 post-ATIMP administration will be assessed using the previous refraction.

⁵ERG assessments may be performed under general anaesthesia if considered appropriate

⁶ HBV testing is only mandatory for participants if required by local practice. Participants with chronic hepatitis B virus infection as indicated by detectable surface antigen will be excluded from the study. For those with negative surface antigen, but positive hepatitis B core antibody, testing will be performed to confirm Hepatitis B viral load following completion of steroid treatment.

*Per section 5.4.2.1 assessments listed as "performed in all participants" must be performed, every effort must be made to perform all other assessments where possible

⁷ Additional monitoring of liver enzymes will be performed following steroid treatment

⁸ Month 3 and 6 assessments should be planned for +3 months and +6 months after the last baseline assessment (Baseline visit 4)

⁹ Patients who screened failed under a previous version of the protocol may be reconsidered for eligibility and will not be required to repeat tests provided these were performed within the visit window from the original screening date.

¹⁰ Treatment Experience interviews will be administered to all subjects either at or within 14 days of the final study visit (month 6 / visit 16), or upon early withdrawal.

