1.3.3. Secondary Efficacy Hypothesis

For the expansion phase, the null hypothesis for each secondary endpoint listed below is that there is no difference between the treated eye in subjects for the immediate treatment at Week 26 and the deferred participant treatment eye in the deferred group during 26-Week deferred period prior to treatment. The alternative hypothesis for each secondary endpoint listed below is that the improvement in the ATIMP treated eye in immediate treatment subjects is greater than that on the deferred participant treatment eye during deferred period prior to treatment.

- a) Central 30-degree hill of vision (V30) in static perimetry using visual field modeling and analysis (VFMA) (Richard Weleber, 2015)
- b) Average threshold in mesopic microperimetry
- c) Maze walk time in Vision Mobility Assessment (VMA) under lux 1 and lux 4, separately
- d) Low Luminance visual acuity (LLVA)
- e) Patient report outcome, Low luminance questionnaire (LLQ) for the assessment of functional vision in low light conditions
- f) Contrast sensitivity (Log CS) as measured by Pelli-Robson
- g) Area of Intact EZ under the fovea from Optical Coherence Tomography (OCT)

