2. GENERAL ANALYSIS DEFINITIONS

2.1. Visit Windows

The following rules are applied to assign actual visits to analysis visit windows. If a subject has two or more actual visits in 1 visit window, the visit closest to the target day will be used as the protocol visit for that visit window. The additional visit(s) will not be used in the summaries or analyses, but they can be used for determination of clinically important outcomes. If two actual visits are equidistant from the target day within a visit window, the later visit is used. All assignments will be made in chronological order. Once a visit date is assigned to a visit window, it will no longer be used for a later time point. If a visit falls outside of the visit window, then this visit will be assigned to the closest window according to the distance to the target day and visit description, if there is no visit assigned to the visit window.

Table 1: Visit Windows

| Dose Escalation Phase, Pediatric Dose Confirmation Phase, and Immediate Treatment Arms of Expansion Phase | | |
|--|----------------------|-------------------|
| Visit Window Label | Time Interval | Target Day |
| Baseline | -6 Months - Day -1 | < Day 1 |
| Day 1 (ATIMP admin.) | Day 1 | Day 1 |
| Day 2 | Day 2 | Day 2 |
| Day 4 | Day 3 – Day 5 | Day 4 |
| Week 1 | Day 6 – Day 10 | Day 8 |
| Week 2 | Day 11 – Day 21 | Day 15 |
| Week 4 | Day 22 – Day 36 | Day 29 |
| Week 6 | Day 37 – Day 56 | Day 43 |

| Week 9 | Day 57 – Day 72 | Day 64 | |
|---|----------------------|---------------------|------------|
| Week 13 | Day 73 – Day 160 | Day 92 | |
| Week 26 | Day 161 – Day 259 | Day 183 | |
| Week 39 | Day 260 – Day 350 | Day 274 | |
| Week 52 | Day 351 – Day 393 | Day 365 | |
| Deferred Treatment Arms of Expansion Phase | | | |
| Period | Visit Window Label | Time Interval | Target Day |
| Deferred Period (prior to treatment) | Baseline | -6 Months - Day 1 | ≤ Day 1 |
| | Week 13 | Day 73 – Day 168 | Day 92 |
| | Week 26 | Day 169 – Day 365 † | Day 183 |
| Post treatment period | Day 1 (ATIMP admin.) | Day 1 | Day 1¶ |
| | Day 2 | Day 2 | Day 2¶ |
| | Day 4 | Day 3 – Day 5 | Day 4¶ |
| | Week 1 | Day 6 – Day 10 | Day 8¶ |
| | Week 2 | Day 11 – Day 21 | Day 15¶ |
| | Week 4 | Day 22 – Day 36 | Day 29¶ |
| | Week 6 | Day 37 – Day 56 | Day 43¶ |
| | Week 9 | Day 57 – Day 72 | Day 64¶ |
| | Week 13 | Day 73 – Day 160 | Day 92¶ |
| | Week 26 | Day 161 – Day 365 † | Day 183¶ |

¶: after ATIMP administration day for deferred subjects

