5.4. Secondary Endpoints

5.4.1. Definition

Secondary efficacy endpoints will be analyzed as change from baseline through the week 26 assessment on treated eye in immediate treatment group and compared with deferred participant treatment eye in deferred treatment group at 26 weeks. Major secondary efficacy endpoints include the following:

- a) Central 30-degree hill of vision (V30) in static perimetry using visual field modeling and analysis (VFMA) (Richard Weleber, 2015)
- b) Average threshold in mesopic microperimetry
- c) Maze walk time in Vision Mobility Assessment (VMA) under 1 lux and 4 lux, where 4 lux will be tested first
- d) Low Luminance best corrected visual acuity (BCVA)
- e) Patient report outcome, Low Luminance Questionnaire (LLQ) for the assessment of functional vision in low light conditions
- f) Contrast sensitivity (Log CS) as measured by Pelli-Robson
- g) Area of Intact EZ under the fovea from Optical Coherence Tomography (OCT)

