5.5. Multiplicity Adjustment

A branched fixed sequence method will be used to control the family-wise type I error rate at 0.05 for testing the primary and key secondary endpoints comparing immediate treatment subjects (pooled low and intermediate doses) with deferred treatment subjects in the expansion phase as illustrated in Figure 3. Alpha of 0.05 will be allocated to the primary endpoint, static perimetry responder by pointwise analysis. If statistically significant, the alpha of 0.05 will be passed down to the first secondary endpoint, V30. If V30 is statistically significant, the alpha of 0.05 will be passed down to the visual mobility assessment. If the visual mobility assessment is statistically significant, MAIA microperimetry and patient report outcome (Impact of Vision Impairment – 'Reading and Accessing Information' domain) will be tested under alpha=0.04 and 0.01, respectively. If one or both endpoints are statistically significant, the remaining alpha will be passed down to test low luminance BCVA, contrast sensitivity and EZ area, conditional on the statistical significance of the prior test. If any of the endpoint(s) are not statistically significant, the allocated alpha for testing cannot be passed and testing will stop after all alpha has been spent.

Figure 3: Illustration of alpha distribution

Key: V30=central 30-degree hill of vision. MAIA =microperimetry

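### As supplied, the deferred-arm schedule has no low luminance visual acuity test between baseline and treatment, although the SAP tests this endpoint against the untreated deferred eye at Week 26

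*Protocol*

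**What the plan says.** **Schedule.** Table 4 of Protocol 5.6 sets the deferred-arm visits. Visits 2-4 are baseline, Visit 5 is Month 3 and Visit 6 is Month 6. Footnote 8 dates the last two from baseline: "Month 3 and 6 assessments should be planned for +3 months and +6 months after the last baseline assessment (Baseline visit 4". Visit 7 is headed "ATIMP admin after M6 assessments", so Visits 5 and 6 are the only scheduled post-baseline visits at which the deferred eye is untreated. The row "Low Luminance Visual Acuity" carries marks at Visits 2, 3, 4, 15 and 16 and nowhere else.

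**Endpoint.** SAP 1.3.3 lists "d) Low Luminance visual acuity (LLVA" among seven secondary endpoints with null and alternative hypotheses. SAP 5.4.1 lists it again as "d) Low Luminance best corrected visual acuity (BCVA". The analysis is change from baseline in the treated eye, "compared with deferred participant treatment eye in deferred treatment group at 26 weeks". SAP 2.1 takes the deferred Week 26 value from "Day 169 – Day 365" of the period before treatment and gives post-treatment visits their own windows, counted from the day of administration.

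**Testing order.** SAP 5.5 controls the family-wise error rate at 0.05. After perimetry response, V30 and mobility, it splits alpha 0.04 / 0.01 between microperimetry and a patient-reported outcome. What remains is "passed down to test low luminance BCVA, contrast sensitivity and EZ area, conditional on the statistical significance of the prior test". Alpha from a non-significant test is not passed on.

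**The concern.** The SAP needs an untreated LLVA value at Week 26 in the deferred arm, and the schedule as supplied does not ask for one. Without it, the randomised comparison for one of the seven listed secondary endpoints has a treated side and no control side. The deferred arm's post-treatment LLVA values cannot stand in, because by then those eyes have been treated.

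There may be a knock-on effect. LLVA is named first in the last step of the alpha chain, and the SAP has no rule for an endpoint that cannot be tested. If it is treated as not significant, contrast sensitivity and EZ area could go formally untested, even though Table 4 schedules contrast sensitivity testing and OCT at Visits 5 and 6.

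**Working it through.** **1. Column check of Table 4.** Each row was split at its cell breaks and matched to the 17 header columns (Visits 1-16 plus the randomisation column).

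| Row | Visits 2-4 | Visit 5 (Month 3, untreated) | Visit 6 (Month 6, untreated) |
|---|---|---|---|
| LLVA | marked | blank | blank |
| Visual acuity | marked | marked | marked |
| Contrast sensitivity | marked | marked | marked |
| Static visual fields | marked | marked | marked |
| Microperimetry | marked | marked | marked |
| OCT | marked | marked | marked |

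The LLVA row has all 17 cells and no stray characters. Every other row marked at all three baseline visits keeps both marks at Visits 5 and 6.

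**2. Search for another instruction.** Protocol 5.4.2.1 lists LLVA with best corrected acuity among tests done in all participants, but that is the baseline list. Protocol 5.4.2.3 refers back to Section 5.6 and, for the deferred arm, gives visits after surgery only. Nothing else schedules LLVA in the deferral period.

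**3. Control values available.** Scheduled untreated post-baseline LLVA values in the deferred arm (up to 16 participants):

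- Week 13: 0 of up to 16
- Week 26: 0 of up to 16

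**4. Consequence for the model.** SAP 5.4.2 models change from baseline on treatment group, baseline value and visit. Baseline enters as a covariate, so a control eye contributes an outcome only if it has a post-baseline value. With none, the treatment term cannot be estimated at any alpha. The general provision for model-based imputation does not help: there would be no scheduled untreated post-baseline LLVA value to fit it to.

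**5. Alpha chain.** The plan's own figure reproduces: 0.04 + 0.01 = 0.05. On the wording of SAP 5.5, LLVA would be tested at 0.05, 0.04 or 0.01, depending on which of the two preceding tests succeed. If LLVA cannot be tested and the order is LLVA, contrast sensitivity, EZ area, the alpha reaching the last two is 0.

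**6. What the missing visits would provide.** The documents give no SD, effect size or power for LLVA, so only standardised differences can be shown. With 16 control and 32 immediate-arm eyes (16 + 16 pooled) and a two-sided normal approximation, the difference detectable with 80% power is

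(z for 1 - alpha/2, plus 0.842) x sqrt(1/16 + 1/32), where sqrt(0.09375) = 0.306.

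- alpha 0.05: (1.960 + 0.842) x 0.306 = 0.86 SD
- alpha 0.04: (2.054 + 0.842) x 0.306 = 0.89 SD
- alpha 0.01: (2.576 + 0.842) x 0.306 = 1.05 SD

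For assumed differences of 0.5, 0.8 and 1.0 SD, power is 37.2%, 74.3% and 90.4% at alpha 0.05, and 17.3%, 51.5% and 75.5% at alpha 0.01. With the visits the test would be modest but usable; without them there is no test.

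**The case against.** **Blank cells in this table are weak evidence.** This is the strongest objection, and much of it stands. Protocol 5.4.2.3 requires PCR sampling in the deferred arm at Month 6 before treatment, among other visits, yet the PCR row is marked only at Week 4 and is as free of stray characters as the LLVA row. The same section requires OCT at every post-treatment visit, and several OCT marks are missing. Screening acuity, required in 5.3.1.6.2, is also unmarked. A reader might therefore take the two LLVA blanks as proof that the test was left out; the supplied text does not prove that. What keeps the point alive is the pattern: LLVA is the only row marked at all three baselines that lacks both untreated visits, and no text elsewhere supplies them.

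**Version.** The SAP is based on protocol v12.0, and the supplied amendment log ends at v11.0. A later version may have added the visits. This stands and cannot be resolved here.

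**The all-participants list.** Table 4's asterisk makes tests on that list mandatory, and the list pairs LLVA with acuity, which is marked at Visits 5 and 6. But the asterisk does not set visits: full-field and pattern ERG are on the same list and are not marked at Visit 6.

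**Blocking.** A reader might infer that contrast sensitivity and EZ area are certainly lost. The documents do not support that. Figure 3 is not shown, the order within the last step rests on word order, the SAP does not say that an untestable endpoint counts as failed, and the issue arises only if the earlier tests succeed.

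**Table 3.** Read by column, its LLVA row also lacks a Month 6 mark for the immediate arms, so a reader might infer that neither arm has a Week 26 value. That row contains stray characters, and nothing here rests on it.

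**Conclusion.** The point holds in limited form. Followed as supplied, Table 4 gives 0 of up to 16 control LLVA values at Week 26, and the LLVA comparison in SAP 1.3.3 and 5.4.1 cannot be estimated. That conclusion rests on the two blanks being real and on no later protocol version having filled them. It does not depend on Figure 3 or on the outcome of other tests.

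The effect on contrast sensitivity and EZ area is conditional: it needs the written order to be the testing order, an untestable endpoint to be treated as not significant, and perimetry response, V30, mobility and at least one of microperimetry and the patient-reported outcome to succeed.

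The primary objective is safety, the expansion phase seeks preliminary evidence of efficacy, and the endpoint comes late in the sequence. The primary efficacy test is unaffected. Should-fix, medium confidence.

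**What to change.** 1. Check the LLVA row at Visits 5 and 6 on the source page of Table 4 and in protocol v12.0. If the visits are marked there, the point closes.
2. If the blanks are real and any deferred participant has yet to reach these visits, mark LLVA at Visits 5 and 6 alongside the acuity testing already done. Cost: one short chart test at two existing visits, at most 2 x 16 = 32 tests.
3. If control LLVA was not collected, amend SAP 5.5 before the final analysis: remove LLVA from the tested sequence or place it last, and report it descriptively as change within treated eyes. Cost: SAP wording only. SAP 1.2 describes the deferral in the past tense, so this is the likelier route.
4. Record that the change rests on data availability alone. Sponsor personnel are not masked (SAP 1.4), and an administrative interim analysis has already summarised the primary and secondary endpoints (SAP 3). A change made for this reason, without regard to observed effects, leaves the family-wise error rate at 0.05.
5. In the same amendment, state the order within the last step in words and say how an endpoint that cannot be tested is handled.

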5.6.1 Early Stopping of Follow-up

If a participant chooses to discontinue their trial treatment, they should continue to be followed up as closely as possible to the follow-up schedule defined in the protocol, providing they are willing. If, however, the participant exercises the view that they no longer wish to be followed up either, this view must be respected. Data already collected will be kept and included in analyses according to the intention-to-treat principle for all participants who stop follow up early.

Participants who stop trial follow-up early may be replaced.

5.6.2 Loss to Follow-up

This is a highly motivated patient group who are likely to remain committed to the research. Continued follow up of all participants will be strongly encouraged whilst being mindful of the importance of ensuring the autonomy of participants in regard to their treatment decisions and willingness to continue to participate in the trial.

5.6.3 Trial Closure

The end of the entire trial is considered the last follow-up visit of the last participant. For each participant, the trial will terminate at the last scheduled visit 12 months following ATIMP administration. The MHRA will be notified of the end of the trial within 90 days of its completion.

5.6.4 Passive/Long Term Follow-Up After the End of the Trial

At the end of this trial, participants will be invited to enrol in a longer term follow-up study to determine longer term safety and efficacy up to 60 months post treatment administration.

5.7 Sample Size

This is a Phase I/II trial to establish safety and assess indicators of potential efficacy of the ATIMP, therefore there is no formal sample size calculation. The trial will enrol up to 71 participants (up to 18 in the dose escalation phase, up to 5 in the dose confirmation in paediatric phase, and up to 48 in the randomised expansion phase), as described in section 4.3.2.2. We estimate that inclusion of up to 53 participants will be sufficient to determine the safety and tolerability of the intervention.

